6.1.3.2 Graphical presentation of results

The individual participant total bacterial load of CFU of potentially pathogenic microorganisms in sputum will be presented.

6.1.4 Supportive analysis

The planned supportive/supplementary analysis will not be performed due to study termination.

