### 4 Rationale

### 4.1 Rationale for study design

This is a non-confirmatory, multi-center, randomized, placebo-controlled, subject- and investigator-blinded, parallel-group trial with a 12-week treatment period. Key efficacy endpoints will be evaluated over the time during the study period.

The design of this study addresses the primary objective to assess the effect of QBW251 compared to placebo administered for 84 days on sputum bacterial colonization. A reduction from baseline in colony forming units of potentially pathogenic microorganisms in spontaneous sputum by one log unit was associated with a significant reduction in risk of exacerbation by approximately 20% in patients with bronchiectasis, which is considered to be clinically relevant (Chalmers et al 2012).

In order to optimize the rigor and integrity of the study and minimize bias, a randomized, subject- and investigator-blinded parallel group is used. The design is well-established in respiratory clinical trials and enables the study treatment to be given for an appropriate and practical length of time to assess the efficacy and safety of the treatment. A parallel study design was chosen because a crossover design assumes patients will return to their own baseline levels of CFU in each period and this may not be the case in the study. It is more versatile in that a stable disease state is not a pre-requisite which is beneficial as also newly diagnosed patients with bronchiectasis may be included.

QBW251, an effective Cystic Fibrosis Transmembrane Conductance Regulator (CFTR) potentiator, is hypothesized to be efficacious in patients with bronchiectasis based on improved mucociliary clearance (MCC), resulting in decreased bacterial colonization, decreased small airway inflammation, improved FEV1 and ultimately fewer exacerbations. Recent evidence suggests the molecular mechanism for reduced mucociliary clearance in bronchiectasis may relate to dysfunction of wild-type and mutated CFTR. Bronchiectasis patients may also have a component of ion channel dysfunction, including CFTR. COPD data suggests that QBW251 may decrease bacterial colonization and small airway inflammation (reduced fibrinogen). In addition, QBW251 demonstrated statistically important improvement in lung function

(FEV1) in cystic fibrosis (CF) following 2 weeks of treatment and in COPD following 4 weeks of treatment.

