# 12.4.1 Definition of primary endpoint(s)

The primary estimand targets the hypothetical effect as if all patients had stayed on treatment for 12 weeks and as if antibiotics other than macrolide had not been available.

- **Population**: patients are defined by the study inclusion and exclusion criteria. The protocol defines the use of allowed maintenance therapy for this target population, as well as medications that are prohibited.
- Variable: change from baseline in bacterial load as measured by the number of colony forming units (CFU/ml) of potentially pathogenic microorganisms in sputum at week 12. A log10 transformation is applied to the CFU counts before forming the change from baseline computing therefore the log ratio to baseline of the bacterial load.
- **Intervention effect** of interest:
- Intake of antibiotics other than macrolide and intake of rescue medication
- Treatment discontinuation or study participation: hypothetical on treatment CFU counts
  - Summary measure: difference in variable means (QBW251 compared with placebo)

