# 12.4.4 Sensitivity and Supportive analyses

The primary estimand described in Section 12.4.1 is complemented by two supplementary estimands. This would allow to assess the robustness of the QBW251 treatment effect on bacterial load drop with and without antibiotics use / pulmonary exacerbations that would be deemed to affect the outcome of interest.

- To estimate the effect of study drug versus placebo without potential confounding due to the antibiotics use for exacerbation. All visits after receiving antibiotics other than macrolide will not be included in the CFU analysis (they will be set as missing). Note that this approach will lead to less data being used than the primary estimand.
- To estimate the effect regardless of antibiotic use. This estimand follows the treatment policy strategy where antibiotics are used as needed basis on top of study treatment as in clinical practice. Thus, the CFU measurements collected during the intake of antibiotics will be included in the analysis. The estimate of treatment actually means (treatment + any antibiotics) in this context.

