6.1.2 Descriptive analysis

The baseline CFU (on log10-transformed scale) of potentially pathogenic microorganisms in spontaneous sputum is defined as the bacterial load collected at baseline (on log10-transfromed scale). "No growth" means there is no growth from the sputum specimen for that visit. The maximum measurable CFU from lab culture will be set as 600,000,000. Thus, any CFU data that is higher than 600,000,000 will be considered as 600,000,000 in reporting.

In order to be included in the sputum analysis, a subject must provide a sufficient sputum sample at screening, and/or at baseline and at least one post-baseline visit.

Summary statistics will be provided by treatment group and visit for the primary variable and will include mean, standard deviation (SD), coefficient of variation (CV), median, minimum and maximum.

6.1.3 Statistical model, assumptions and hypotheses,

The planned Bayesian repeated measures model will not be performed due to study termination and in absence of informative data, the original PoC criteria will not be evaluated as well.

The primary analysis will include all available data from subjects in the PD analysis set.

Differences between treatment groups (QBW251 versus placebo) for change from baseline in CFU counts (on log10-transformed scale) will be analyzed using a mixed model for repeated measurements (MMRM). The analysis will be carried out using SAS proc mixed procedure with Unstructured covariance structure, with treatment group and visit as fixed effects, baseline log (CFU count), status of macrolides use at screening as covariates, adjusting for effect of treatment*visit, baseline value*visit. Contrasts for treatment differences will be provided together with two-sided 80% confidence intervals.

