6.1.3.1 Handling of missing values/censoring/discontinuations

The CFU counts assessed within 2 weeks after bronchiectasis exacerbations or during or after last dose of antibiotics will not be included in the primary analysis. This is because of the potential confounding effect were expected from the use of antibiotics.

However, the CFU counts at the following visits (if there is no antibiotics use and no bronchiectasis exacerbation) are assumed not to be confounded and will be included in the primary analysis.

Efficacy data collected during intake of rescue medication will be used for analysis, since no confounding effect is expected from the use of rescue medication. Of note, on days of rescue medication intake participants are instructed to fill in the e-diary for that day prior to intake of rescue medication.

Missing on-treatment data related to the primary endpoint will not be explicitly imputed. The repeated measures analysis includes all available information in terms of measurements at all times. If endpoint measurements are missing at random, an analysis of the available data provides consistent estimates of model parameters.

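### SAP 6.1.4 drops the planned treatment-policy CFU analysis, leaving no check on how the one remaining modelled contrast depends on its exclusion rule

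*SAP*

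**What the plan says.** **Primary estimand.** Protocol 12.4.1 targets a hypothetical effect: everyone stays on treatment for 12 weeks, "as if antibiotics other than macrolide had not been available". Protocol 12.4.2 and 12.4.3 carry this out by leaving out CFU values near exacerbations and near antibiotics other than macrolides. A valid unscheduled assessment at that time point may be used.

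**Planned check.** Protocol 12.4.4 adds two supplementary estimands to examine robustness. One discards every visit after non-macrolide antibiotics. The other goes the opposite way: "This estimand follows the treatment policy strategy where antibiotics are used as needed basis on top of study treatment as in clinical practice", so that "the CFU measurements collected during the intake of antibiotics will be included in the analysis".

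**What the SAP keeps.** SAP 6.1.3 replaces the Bayesian model with an MMRM on change in log10 CFU and states: "Contrasts for treatment differences will be provided together with two-sided 80% confidence intervals". SAP 6.1.3.1 sets the exclusion: "CFU counts assessed within 2 weeks after bronchiectasis exacerbations or during or after last dose of antibiotics will not be included" in the primary analysis. That sentence has neither the macrolide exception nor the unscheduled-assessment provision.

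**What the SAP drops.** SAP 6.1.4 reads: "The planned supportive/supplementary analysis will not be performed due to study termination". Modelling of the secondary endpoints and all exacerbation analyses are cancelled too.

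**The concern.** The retained contrast depends on a rule that removes values after events occurring since randomisation. Those events are plausibly related to the outcome. Protocol 4.1 says that a CFU reduction "by one log unit was associated with a significant reduction in risk of exacerbation by approximately 20" percent, and it expects the drug ultimately to lead to fewer exacerbations. If the drug works as hypothesised, the rule may remove more values on placebo than on QBW251.

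The protocol provided for this by planning a second run with the values kept. The SAP withdraws that run, and termination is the only reason given. Termination could explain giving up an analysis that needs more data or a larger sample. It does not explain fitting the MMRM to the reduced data while declining to fit it to the fuller data. What is lost is the ability to see whether the reported difference depends on a few exclusions.

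**Working it through.** **1. The plan's own figure.** Protocol 12.8.1 assumes 60 completers (30 per arm), a difference of 1.5 log10, an SD of 2.8 and a 10% level.
- Standard error: 2.8 × √(2/30) = 0.723.
- One-sided power: Φ(1.5/0.723 − 1.2816) = Φ(0.793) = 78.6%, against the stated 79%. The two-sided version gives 66.6%, so the 10% is one-sided.
- Randomised: 60/0.84 = 71.4, rounded up to 72, as stated.

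The SD of 2.8 is therefore used in step 5.

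**2. Is the withdrawn run feasible?**
- Sputum culture is scheduled at Days 28, 56 and 84 (Protocol Table 8-1).
- Patients with an exacerbation stay on study treatment (Protocol 3.1), so their scheduled samples continue.
- At scheduled visits, the treatment-policy run uses every value that the SAP's primary analysis uses and adds back those the rule removes. It needs no new data, and its sample is never smaller.

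**3. How often could the rule apply?** The input is the background rate in Protocol 1.1, 1.3 to 3 exacerbations per patient-year. Under an assumed constant hazard, P = 1 − exp(−rate × days/365.25).

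| Window | Rate 1.3 | Rate 3 |
|---|---|---|
| Any event in 84 days | 25.8% | 49.8% |
| Event in last 14 days (the stated two weeks) | 4.9% | 10.9% |
| Event in last 28 days (assumed) | 9.5% | 20.5% |

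The 28-day row assumes a 14-day antibiotic course followed by the two weeks. The documents give no course length. The last two rows approximate the share of week-12 values removed.

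**4. What could this do to the contrast?** In simple means, treatment-policy difference minus kept-data difference = (share removed on QBW251 − share removed on placebo) × (mean of removed values − mean of kept values). The inputs below are illustrative, because the documents give none.
- Equal removal in both arms: 0.
- 10% on QBW251, 20% on placebo, removed values 1 to 3 log10 lower: (0.10 − 0.20) × (−1 to −3) = +0.1 to +0.3 log10, less favourable to QBW251.
- The reverse imbalance: −0.1 to −0.3 log10.

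**5. Against what precision?** The 80% half-width is 1.2816 × 2.8 × √(2/n), with n per arm. The documents do not give the number randomised at termination.

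| n per arm | 7 | 10 | 15 | 30 |
|---|---|---|---|---|
| Half-width (log10) | 1.92 | 1.60 | 1.31 | 0.93 |

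The illustrated shifts are well inside these widths.

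**6. The two exclusion rules side by side.** The protocol's rule is limited to antibiotics other than macrolides and admits a valid unscheduled assessment. The SAP's sentence does neither. Macrolide use is a randomisation stratum (Protocol 6.3.2) and a covariate in the SAP's MMRM.

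**The case against.** The strongest reply is that the exclusion is not the SAP's invention. It implements the protocol's hypothetical estimand. The treatment-policy run answers a different question, the effect of study drug plus any antibiotics, as Protocol 12.4.4 itself says. A gap between the two results would not test missing-at-random and would not show bias in the primary. All of this stands. A reader might infer that the retained contrast is biased, but the documents do not support that. The MMRM uses baseline and earlier CFU, and the removal may be balanced.

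A reader might also infer that no other between-arm information survives. That is not so. By-arm CFU summaries, the clearance table (based on all participants with microbiology results at each visit) and individual CFU profiles remain. Concomitant therapies are listed by arm and subject, so affected values could be traced with effort. None of these gives the contrast without the exclusions, and none is specified to count them.

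Nor would the rerun restore a full randomised comparison. The PD set is analysed by treatment received and requires baseline and post-baseline data. Patients who stop treatment return for the end-of-study assessments, where no sputum is scheduled.

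Finally, the study is non-confirmatory, its proof-of-concept criteria will not be evaluated, and the reduction in scope is openly declared. That limits the weight of the point. It does not supply a reason for dropping this particular run.

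**Conclusion.** The point holds as a matter of reporting. A prespecified robustness analysis was withdrawn for a reason that does not bear on it, and the only modelled contrast left has no companion showing its dependence on the exclusions.

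The rule may remove about 5% to 11% of week-12 values on the stated two-week window, or 9% to 21% on the assumed 28-day window. Both ranges rest on a constant hazard and a background rate. That rate may be too high here: Protocol 5.1 requires clinically stable patients and only one exacerbation since January 2019. The effect on the contrast is unknown. It is zero under balanced removal and small beside the interval width in the illustrated imbalance.

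The difference in exclusion wording between SAP 6.1.3.1 and Protocol 12.4.2 and 12.4.3 is a separate defect. A reader might infer that all values from patients on maintenance macrolides will be dropped. The literal sentence permits that, but the SAP keeps macrolide status as a covariate, so the intention is not established. The passages need to be reconciled.

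**What to change.** Amend SAP 6.1.4 along these lines:

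> The MMRM of Section 6.1.3 will be repeated as a supplementary treatment-policy analysis. It includes all on-treatment CFU values from scheduled visits, with their 3-day sputum return window, regardless of antibiotic use or exacerbation. The treatment difference and two-sided 80% confidence interval will be shown next to the primary result. Extra samples from exacerbation visits are not mapped to scheduled visits. The number of CFU values excluded from the primary analysis will be tabulated by arm and visit.

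The other supplementary estimand may stay cancelled. It uses less data than the primary, so small numbers are a fair reason to omit it.

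In SAP 6.1.3.1, state whether the protocol's macrolide exception and unscheduled-assessment provision still apply. If they do not, record the change and the reason.

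The cost is one further model run with one filter switched off, one count table and a wording correction. The downside is one more exploratory and imprecise interval, which addresses a different estimand and does not cover treatment discontinuation. If the rerun is still declined, the count table should be produced, and the report should say that the contrast is conditional on the exclusion rule and on missing at random.

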6.2 Secondary objectives

6.2.1 Variables

The secondary pharmacodynamics and efficacy endpoints are as follows:

- Proportion of subjects with absence of any CFU of potentially pathogenic bacteria in sputum culture.
- Changes from baseline in the Quality of life Questionnaire for Bronchiectasis (QOL-B) (Respiratory symptoms domain).
- Change from baseline in fibrinogen plasma concentration.
- Change from baseline in rescue medication use (salbutamol/albuterol)
- Change from baseline in pre- bronchodilator FEV1, FVC measured by spirometry.
- Change from baseline in airway wall and lumen parameters along with extent of global and

regional air trapping, as measured by HRCT.

6.2.2 Descriptive analyses

Summary statistics of change from baseline for each secondary efficacy endpoint will be provided by treatment group and visit for all secondary endpoints, if data allows.

6.2.1 Statistical model, assumptions and hypotheses

The modeling for secondary pharmacodynamics objectives planned as per protocol will not be performed due to the study termination.

The secondary objective analysis will include all available data from subjects in the PD analysis set

Baseline secondary efficacy parameters (QOL-B, fibrinogen, FEV1, FVC) is defined as the measurement taken prior to the first dose of study drug (Day 1). If this assessment is missing (or is not confirmed to be pre-dose), then the screening assessment will be considered as baseline.

For spirometry data, only "acceptable" spirometry data will be included for analysis. In case 2 pre-dose spirometry assessments at -45min and -15min are performed, the first attempt (-45min) will be used for analysis if it's acceptable; if the first attempt is not acceptable, then the second attempt (-15min) will be used; if the second attempt is also not acceptable, then there would be no data available for that timepoint.

Changes from baseline in the Quality of life Questionnaire for Bronchiectasis (QOL-B) (Respiratory symptoms domain)

For Quality of Life Questionnaire for Bronchiectasis (QOL-B), the summary statistics for change from baseline in Respiratory Symptoms scale will be reported by treatment group and visit. The Respiratory Symptoms scale scores, with higher scores representing fewer symptoms or better functioning. Refer to Table 6-1 for details of response value and the corresponding scores for QOL-B Questionnaire (Respiratory symptoms domain) during reporting.

Table 6-1 Scoring algorithm for QOL-B Questionnaire (Respiratory symptoms domain)

QUESTION NUMBER	QUESTION SHORT NAME	QUESTION NAME	OPTIONS(CHAR)	OPTIONS(NUMERIC)
29	BQOL129	Congestion in Chest	A lot	1
			A moderate amount	2
			A little	3
			None at all	4
30	BQOL130	Coughing During Day Time	A lot	1
			A moderate amount	2
			A little	3
			None at all	4

31	BQOL131	Cough Up Sputum	A lot	1
		•	A moderate amount	2
			A little	3
			None at all	4
32	BQOL132	Sputum Observation	Clear	5
			Clear to yellow	4
			Yellowish-green	3
			Brownish-dark	2
			Green with traces of blood	
			Don't know	1
33	BQOL133	Shortness Breath	Always	0
33	BQOE133	When Active		1
			Often	2
			Sometimes	3
			Never	4
34	BQOL134	Have You Had Wheezing	Always	1
			Often	2
			Sometimes	3
			Never	4
35	BQOL135	Have You Had Chest Pain?	Always	1
			Often	2
			Sometimes	3
			Never	4
36	BQOL136	Shortness of Breath When Walking	Always	1
		, , , , , , , , , , , , , , , , , , ,	Often	2
			Sometimes	3
			Never	4
37	BQOL137	Woken Up Due to Coughing	Always	1
			Often	2
			Sometimes	3
			Never	4
37	BQOL137	Woken Up Due to Coughing	Always	1
			Often	2
			Sometimes	3
			Never	4

Proportion of subjects with absence of any CFU of potentially pathogenic bacteria in sputum culture.

The number and percentage for participants with no CFU in sputum will be tabulated by treatment arm and visit. Percentages will be based on the number of participants for whom microbiology results exist per visit.

Change from baseline in rescue medication use (salbutamol/albuterol)

Baseline rescue medication use is defined as the average number of puffs per day in the screening period and the morning record at Day 1. All days with data will be used for calculating the baseline value.

The total number of puffs of rescue medication will be divided by the total number of (full or half) days with non-missing rescue data to derive the mean daily number of puffs of rescue medication taken for the patient for each given visit interval. If the number of puffs is missing for part of the day (either morning or evening) then a half day will be used in the denominator. No imputation will be used for missing rescue therapy. Any values >48 for the number of puffs of rescue medication in a 12 hour period will be set to missing. These high numbers are not realistic and could impact the analysis.

If a participant has only 0 to 6 days of data recorded, the baseline will be set to missing. Participants must have at least 7 days of rescue medication data recorded to have a baseline level calculated

The post-baseline treatment period is defined as the period from the evening record of Day 1 up to the morning assessment following the day of the last dose of double-blind treatment. Missing diary data will not be imputed. For the derivations of on-treatment mean weekly and mean monthly number of puffs, only values from Day 1 up to the date of last dose of double-blind treatment will be considered.

The daily number of puffs will be averaged for each week (Week1, Week2, etc). A patient needs to have at least 4 days of data in any week in order for the mean score to be calculated.

Monthly means over a 4-week period will also be calculated. A patient needs to have at least 3 weekly means in that month in order for the monthly mean to be calculated. Mean daily number of puffs will be summarized descriptively by monthly interval.

Changes from Baseline in airway wall and lumen parameters along with extent of global and regional air trapping, as measured by HRCT

The baseline is defined as the HRCT performed after participants have passed all the other screening criteria and prior to randomization. Summary statistics of change from baseline in airway wall and lumen parameters will be provided. Global and region air trapping changes will also be summarized.

Listings for participants' air trapping measured by HRCT will also be provided.

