# 12.4.3 Handling of missing values/censoring/discontinuations

Since the primary estimand is related to an effect outside of antibiotics intake, the CFU counts assessed within 2 weeks after pulmonary exacerbations or during or after last dose of antibiotics, other than macrolide, would not be included in the primary estimand. They will be excluded from the primary estimand, if a valid unscheduled assessment did not happen at the time point for the primary analysis. This is because of the potential confounding effect were expected from the use of antibiotics.

If a valid unscheduled assessment happened at the time point for the primary analysis, then the CFU data collected during the unscheduled visit will be included in the primary estimand. Details about the definition of unscheduled visit is provided in the site manual.

However, the CFU counts at the following visits (if there is no antibiotics use and no pulmonary exacerbation) are assumed not to be confounded and will be included in the primary estimand of interest.

For the primary analysis, only on-treatment data (from date of first randomized dose up to 1 day after date of last randomized dose) will be used as the estimand specifies a hypothetical on treatment effect. Missing on-treatment data related to primary endpoint will not be explicitly imputed. If endpoint measurements are missing at random, an analysis of the available data provides consistent estimates of model parameters.

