# 12.5 Analysis of secondary endpoints

# 12.5.1 Efficacy and/or Pharmacodynamic endpoint(s)

# 12.5.1.1 Proportion of patients with absence of any CFU or CFU counts below the limit of quantification

The proportion of patients with absence of any CFU or CFU counts below the limit of quantification at week 12 will be analyzed using a logistic regression. The model will include treatment, baseline macrolide use as fixed class effects and the number of bronchiectasis exacerbations in the 12 months prior to screening as a categorical variable. The estimated odds ratios will be displayed along with the associated 80% confidence intervals.

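### The SAP's clearance table counts cultures that exacerbation antibiotics may have made negative, although the primary analysis excludes the same cultures as confounded; it should be shown both ways

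*SAP*

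**What the plan says.** **Clearance table.** SAP 6.2.1 (Statistical model, assumptions and hypotheses) states: "The number and percentage for participants with no CFU in sputum will be tabulated by treatment arm and visit". The denominator follows: "Percentages will be based on the number of participants for whom microbiology results exist per visit". For secondary endpoints in general the same section says: "The secondary objective analysis will include all available data from subjects in the PD analysis set". It also drops the planned secondary modelling because the study was terminated, so this table is the only clearance result.

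**Primary analysis.** SAP 6.1.3.1 states: "The CFU counts assessed within 2 weeks after bronchiectasis exacerbations or during or after last dose of antibiotics will not be included". The exclusion is limited to the primary analysis, and the reason given is: "This is because of the potential confounding effect were expected from the use of antibiotics". Protocol 12.4.3 ties the rule to the primary estimand in the same way ("Since the primary estimand is related to an effect outside of antibiotics intake"). Protocol 12.4.2 and 12.4.3 exempt macrolides; SAP 6.1.3.1 does not repeat the exemption.

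**Antibiotics on study.** Protocol 3.1, 6.2.3 and Table 6-2 allow antibiotics for exacerbations, with study treatment continuing. In SAP Table 4-1 the only deviation code that removes a subject from the PD analysis set is missing informed consent.

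**Definition of clearance.** Protocol Table 2-1 and SAP Table 1-1 count only the absence of any CFU. Protocol 12.5.1.1 analyses "The proportion of patients with absence of any CFU or CFU counts below the limit of quantification at week 12". SAP 6.1.2 describes no growth, but the SAP does not say how a count below the limit of quantification is classified.

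**The concern.** The first secondary endpoint is a yes/no reading of the cultures that feed the primary endpoint. The SAP judges some of them unfit for the primary comparison because antibiotics may have lowered the count, and then lets them into the clearance table, where a sterilised sample is a success. The SAP does not say this outright; it follows from its silence on antibiotics together with its use of all available data.

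If one arm has more exacerbations, it receives more antibiotics and gains more antibiotic-driven negatives. The protocol's hypothesis is that QBW251 leads to fewer exacerbations (4.1), in which case the distortion works against the drug. Chance imbalance would do the same in either direction, and SAP 6.2.2 (PK/PD relationships) itself refers to a low sample size after termination.

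The reader would have little to check this with. The exacerbation analyses (SAP 6.3) and the supplementary analyses (SAP 6.1.4) are cancelled. Concomitant medication is still summarised by arm (SAP 7.2), but it is not linked to the cultures.

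**Working it through.** **Plan's own figure.** The documents state no figure for clearance. The only relevant numbers are the sample-size figures in protocol 12.8.1, and they reproduce: 60/(1 − 0.16) gives 72 randomised, and 30 per arm with a difference of 1.5, SD 2.8 and one-sided 10% gives 78.6% power against the stated 79%. They concern the primary endpoint and are used here only for the planned 30 completers per arm.

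**Step 1: share of patients in the window at a visit.** Protocol 1.1 gives about 1.3 to 3 exacerbations per patient-year. The window is 14 days (the two-week rule alone) or, assuming a 10 to 14 day antibiotic course plus two weeks, 24 to 28 days. Share e = 1 − exp(−rate × days/365.25).

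| Rate per year | 14 days | 24 days | 28 days |
|---|---|---|---|
| 1.3 | 4.9% | 8.2% | 9.5% |
| 3 | 10.9% | 17.9% | 20.5% |

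**Step 2: effect on the table.** Let c be the culture-negative rate outside the window and s the rate inside it. The observed clearance rate in an arm is (1 − e)c + e·s. With no true drug effect, the observed difference (drug minus placebo) is

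(e_drug − e_placebo) × (s − c).

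It is zero if exposure is equal or if s = c. Assumed ranges, because the documents give none: c = 5% to 15%, s = 30% to 60%.

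| In window, placebo vs drug | Smallest (c = 15%, s = 30%) | Largest (c = 5%, s = 60%) |
|---|---|---|
| 10% vs 8% | −0.02 × 0.15 = −0.3 points | −0.02 × 0.55 = −1.1 points |
| 21% vs 10.5% | −0.105 × 0.15 = −1.6 points | −0.105 × 0.55 = −5.8 points |

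The negative sign favours placebo, which is the arm with more exposure in these scenarios. Within this model, leaving out the window gives zero, because c is assumed unrelated to exacerbation. The objection below takes up that assumption.

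**Step 3: scale.** With 30 per arm, one reclassified patient moves an arm by 1/30 = 3.3 points, and by more in a smaller sample. For assumed rates of 20% vs 10% with 30 per arm, the standard error of the difference is √(0.2 × 0.8/30 + 0.1 × 0.9/30) = 9.1 points, so an 80% interval is about ±12 points.

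**Limit of quantification.** No limit and no frequency of counts below it are given, so this effect cannot be computed.

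**The case against.** The case against has five parts.

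- **Not a SAP departure.** Protocol 12.5.1.1 has no antibiotic exclusion for this endpoint. A reader might infer that the SAP introduced the problem; the documents do not support that. This part stands.
- **All cultures is a legitimate estimand.** Protocol 12.4.4 includes a treatment-policy estimand that keeps measurements taken during antibiotic use. This stands, and it is why that row should remain. It also supports a label, because the primary result beside it answers a different question.
- **Exclusion can itself be selective.** Dropping cultures after exacerbations conditions on a post-randomisation event. Protocol 1.1 and 4.1 link infection and bacterial load to exacerbations, so the excluded patients may be poor clearers. If placebo has more of them, exclusion raises placebo clearance. A raw percentage lacks the missing-at-random support of the primary repeated-measures model. This stands, and it rules out replacing one table with the other.
- **Size.** A reader might infer that a true effect would be largely hidden. Assuming clearance of 20% vs 10%, 2 vs 3 exacerbations a year, a 21 to 28 day window and 50% to 80% of cultures in it negative, a true 10 points shows as 4.1 to 6.9. But 3 a year is the top of the protocol's range. With 1.3 a year and a 20% reduction, the same formula gives 8.0 to 8.9. Even equal rates of 3 a year give 7.9 to 8.4, so part of the loss is plain dilution. The clearance and negativity figures have no source in the documents.
- **Little rests on the table.** It carries no test, interval or decision, and sampling noise exceeds the distortion. This lowers the priority, but as the only clearance result its percentages will still be compared by arm.

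A reader might also infer that omitting counts below the limit of quantification adds to the bias. The documents show no link to exacerbations, and the SAP matches protocol Table 2-1; the conflict lies inside the protocol. Counting such results as cleared could even add antibiotic-suppressed counts to the all-cultures row.

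**Conclusion.** The point holds as an inexpensive improvement; the table is not wrong as written. As specified, it counts antibiotic-affected negative cultures as clearance, while the primary analysis excludes counts from the same cultures as confounded. The gap is shared by protocol and SAP.

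If antibiotic exposure differs between arms, the table favours the more exposed arm. The distortion is zero with equal exposure and roughly 0.3 to 6 points in the scenarios above. Only the exacerbation range comes from the documents; the course length, the difference in exposure between arms and the culture-negative rates inside and outside the window are assumptions. A firm statement that the table will hide a drug effect is not supported.

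The conflict over counts below the limit of quantification is a separate clarification.

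**What to change.** 1. In SAP 6.2.1, report clearance by arm and visit in two labelled rows: (a) all cultures, regardless of antibiotics; (b) excluding cultures in the exacerbation/antibiotic window used for the primary analysis.
2. For row (b), use the macrolide exemption of protocol 12.4.2 and 12.4.3. Applying SAP 6.1.3.1 literally could remove maintenance-macrolide users.
3. Give the number of cultures excluded per arm and visit, and note that neither row should be read alone.
4. Separately, reconcile protocol Table 2-1 and the SAP (absence of any CFU) with protocol 12.5.1.1 (absent or below the limit of quantification), and state how counts below the limit are classified.

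**Cost.** One extra table row and a count of exclusions, from flags the primary analysis already needs, plus a sentence on classification. Row (b) has a smaller denominator and conditions on events after randomisation.
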